The Apos Device. (a) Biomechanical device comprising two individually calibrated elements and a foot-worn platform. The elements are attached to a platform under the hindfoot and forefoot regions. (b) The biomechanical elements are available in different degrees of convexity and resilience. (c) The specially designed sole of the platform includes two mounting rails and a positioning matrix to enable flexible positioning of each biomechanical element. [Elbaz, 2014].

Figure 2. The sham device

CONFIDENTIAL

This material is the property of the NYU School of Medicine and Langone Medical Center. Do not disclose or use except as authorized in writing by the study sponsor

Objectives and Hypothesis of Study

1. The primary objective is to evaluate the efficacy of AposTherapy® at 6 months, with the primary efficacy assessment based on improvement in knee pain score and improvement in function in patients with knee OA. The hypothesis is that patients fitted with the calibrated AposTherapy® device will demonstrate an improvement in knee pain intensity and improvement in function compared to patients who are fitted with a sham-placebo Apos device.
2. After completion of 6 months of therapy, patients will be un-blinded to their group allocation and the second phase of the study will commence, including the following aims:
 - a. To evaluate the long-term (12 months) effect of AposTherapy® on the level of pain and the level of function of patients with knee OA. We hypothesize that patients will maintain the diminished levels of pain and improved function.
 - b. To evaluate the changes in the level of pain and the level of function of patients that were originally allocated to the control group and will now cross-over and commence AposTherapy® treatment for 6 months. We hypothesize that patient will report an improvement in the level of pain and improvement in function following 6 months of treatment.

Primary Efficacy Endpoints

- Phase I:
 - Improvement in knee pain score and improvement in function, as measured by change from baseline Western Ontario and McMaster University (WOMAC) score to 6 months post treatment.
- Phase II:
 - Long-term effect (12 months) of AposTherapy on pain and function, as measures by WOMAC, of patients with knee OA
 - Improvement in knee pain and knee function, as measured by WOMAC, of patients with knee OA that were allocated to the sham control group and have crossed-over to the active group, receiving AposTherapy for 6 months.

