At each follow-up visit, subjects will be asked on their use of any rescue medications or therapy for their knee pain. Rescue medications or therapy will include, but are not limited to, NSAIDs, physical therapy and surgical interventions. While participating in the study, subjects should refrain from taking corticosteroid and/or hyaluronic acid injections. Subjects will also be asked about their compliance with the device (ex. how long and how often the device was worn?). Research personnel will collect and record such data and note when the subject had the intervention.

Additionally, at each follow-up visit, subjects will be asked to report any changes in their knee symptoms. This change in symptoms can include, but are not limited to, pain, swelling, redness, or any overall changes in their health since the screening/baseline visit. Research personnel will collect and record such data and note when these changes occurred.

II. CHARACTERISTICS OF THE RESEARCH POPULATION

Number of Subjects

A total of one-hundred and twenty (120) patients will be enrolled in this study (60 patients assigned to each group).

Gender of Subjects

Men and women will be included in this study.

Age of Subjects

Subjects will be at least 45 years of age and no older than 75 years of age

Racial and Ethnic Origin

There are no enrollment restrictions based on race or ethnic origin.

Inclusion Criteria

- Males and females between the ages of 40-75;
- Patients suffering from symptomatic unilateral or bilateral knee OA at the medial compartment for at least six months;
- Fulfilling the ACR clinical criteria;
- Having radiographically assessed OA of the knee with a Kellgren-Lawrence grade more than or equal to grade 2; and,
- Having VAS-Pain ≥ 3 , on a scale between 0-10.
- Patients who have a shoe size between US 4 and US 12

Exclusion Criteria

- Patients suffering from acute septic arthritis.
- Patients who received a corticosteroid injection within 3 months of the study.

CONFIDENTIAL

This material is the property of the NYU School of Medicine and Langone Medical Center. Do not disclose or use except as authorized in writing by the study sponsor

- Patients who received hyaluronic acid (HA) injections within 6 months of the study
- Patients suffering from avascular necrosis of the knee.
- Patients with a history of knee buckling or recent knee injury.

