- Patients who have had a joint replacement or other major surgery to the knee, hip or ankle (ipsilateral or contralateral side).
- Patients suffering from neuropathic arthropathy.
- Patients with an increased tendency to fall.
- Patients exhibiting a lack of physical or mental ability to perform or comply with the study procedure.
- Patients with a history of pathological osteoporotic fracture.
- Patients suffering from symptomatic degenerative arthritis in lower limb joints other than the knees.
- Patients with referred pain in the knees from primary back or hip joint pain.
- Patients with neurological deficits to the lower extremity (ex. foot drop)
- Patients whose shoe size is less than US 4 and greater than US 12
- Patients who have had arthroscopy within 6 months of the study
- Patients with inflammatory arthropathy
- Patients with any central nerve system disease/neurological problem (i.e. Parkinson's, post CVA (stroke), etc.).

Vulnerable Subjects

We do not intend to enroll vulnerable subjects.

Subject Withdrawal

Patients are free to withdraw at any time from the study. While participating in the study, patients should avoid any other treatment modality apart from rescue pain medication (Acetaminophen/Paracetamol) as long as it is possible. If patients require injection therapy or surgery on the study knee(s) during the course of the study, the patient will be withdrawn from further data collection.

III. METHODS AND PROCEDURES

Sample Size Analysis

Assuming normality on the data, we calculated the statistical power for various detectable effect sizes listed in Table X using PASS 2011 software (http://www.ncss.com/download_PASS11.html). The analysis of power is performed conservatively by assuming the largest variability in pain scores observed in the preliminary data (e.g., reduction of pain scores of 3.0 in active group and 0 of control group with a pooled standard deviation of 3.60 corresponds to an effect size of 0.8. After accounting for a 10% loss to follow-up we would expect to enroll 60 patients in each group for a total of 120 patients. With 120 samples (60 each), the two-sided t-test will have 80% power at the 0.05 significance level to detect differences of pain score of 0.8 SD units between control and case [Bar-Ziv, 2013].

Methods and Procedures

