Patients that were allocated to the control group will receive the AposTherapy® device and treatment. The device, with calibrated elements, will be individually calibrated to the patients according to his/her clinical condition. During their daily routine, patients will be asked to wear their custom-worn device for approximately 2 hours per day, throughout the study duration, starting with less than an hour of walking around the house and gradually increasing wearing time to outdoor walking. Patients that crossed from the control group to the active group will be assessed after 3 months and 6 months from commencement of phase II. The results of the 6 months will serve as their new baseline results for phase II of the study. Patients will be asked to come to follow-up visits at the treatment center (located at [name]) at the following time points: 27 weeks from original baseline, 36 weeks from original baseline, 42 weeks from original baseline, and 52 weeks from original baseline. During these visits the biomechanical device will be adapted according to the clinical needs of the patient.

CONFIDENTIAL

This material is the property of the NYU School of Medicine and Langone Medical Center. Do not disclose or use except as authorized in writing by the study sponsor

Study schedule:

Study Periods	Screening	Treatment, Intervention Period									
		1	2	3	4	5	6	7	8	9	10
Time (week)	-2	0	3	7	12	18	24 – final assessment for phase I, un-blinding patients, cross-over design and commence of phase II	27 – only for patients that crossed-over from the control group to the intervention group	36	42	52
Patient Information and Informed Consent (at NYULMC)	X										
Demographics (at NYULMC)	X										
Medical History (at NYULMC)	X										
In- /Exclusion Criteria (at NYULMC)	X										
Full Research Assessment (Physician) (at NYULMC)	X				X		X		X		X
Radiography (at NYULMC)	X										
Randomization (at NYULMC)	X										
Concomitant Therapy (at NYULMC)	X				X		X		X		X
Primary Variables (at NYULMC)	X				X		X		X		X
Secondary Variables (at NYULMC)	X				X		X		X		X
Adverse Events (at NYULMC)					X		X		X		X
Administer Medical Device (at Apos Center)		X					X – for patients who crossed-over from control to active				
Adjustment Medical Device (at Apos Center)			X	X	X	X	X – active group	X	X	X	X

CONFIDENTIAL

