This material is the property of the NYU School of Medicine and Langone Medical Center. Do not disclose or use except as authorized in writing by the study sponsor

Data Analysis

Phase I:

- Primary outcome measures will include comparing scores at baseline and the following study time points (baseline, 3 months and 6 months) obtained from the WOMAC. The WOMAC is a validated outcomes assessment used to measure patients' opinion about their knee and associated problems.
- Secondary outcome measures will include comparisons of all measured variables between baseline and all time points including VAS score, SF-36 score, improvement and maintenance in knee function using physical examination findings (these include, but are not limited to: Pain, Knee Effusion, Ligament Stability, Stability, Strength, Range of Motion, Sensation, Posture/alignment); and monitoring usage of rescue medications or NSAIDs. All data will be obtained from the completed case report forms that are being utilized for this study.

Phase II:

- Original active group – evaluating the changes in pain, function, quality of life and usage of rescue medications or NSAIDs following 12 months of therapy.
- Cross-over group – comparing scores at baseline and the following study time points (baseline, 3 months and 6 months) obtained from the WOMAC, SF-36, knee function and usage of rescue medications or NSAIDs.

DATA SAFETY MONITORING PLAN (DSMP)

I. Study Monitoring

The principal investigator, [name], will be the data safety monitor for this project. After a three (3) months follow-up period, [name] will review the data for SAE's, protocol deviations and other issues. If it is determined that certain events occur above an expected rate (i.e. increased knee pain), then enrollment will be stopped.

II. Types of Data

Under this DSMP, the following data/events will be captured and documented:

- Duration of AposTherapy® use;
- Monitoring of patient falls;
- Patient Outcomes Assessments;
- Reportable and/or adverse events
- Protocol Deviations

III. Responsibilities and roles for gathering, evaluating and monitoring the data:

Principal Investigator

After a three (3) months follow-up period, the PI will meet with any co-investigators and the Research Coordinator to discuss the current findings and analysis. During these meetings, the PI will also be responsible for verifying data accuracy, and compliance with the study protocol.

Research Coordinator

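### Patients who need an injection or surgery on the study knee drop out of data collection, so the 6-month comparison can be biased if these withdrawals, or the course of the withdrawn patients, differ by arm

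*Combined protocol and SAP*

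**What the plan says.** The rule for enrolled patients is in section II, Subject Withdrawal: should they "require injection therapy or surgery on the study knee(s) during the course of the study, the patient will be withdrawn from further data collection". It ends outcome collection, not only study treatment, and it runs through both phases.

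The Phase I primary endpoint (section I, Primary Efficacy Endpoints) is the "change from baseline Western Ontario and McMaster University (WOMAC) score to 6 months post treatment". Section III, Data Analysis, says "Primary outcome measures will include comparing scores at baseline and the following study time points (baseline, 3 months and 6 months"), taken from the WOMAC. It names no analysis set, no rule for analysing patients as randomised, no missing-data method and no handling of these events. The only allowance for losses is in Sample Size Analysis: "After accounting for a 10% loss to follow-up we would expect to enroll 60 patients in each group".

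Two statements under Outcome Measure Evaluation Criteria also bear on this. Patients are asked at each follow-up visit about rescue: "Rescue medications or therapy will include, but are not limited to, NSAIDs, physical therapy and surgical interventions", and "Research personnel will collect and record such data and note when the subject had the intervention". They are also told that "subjects should refrain from taking corticosteroid and/or hyaluronic acid injections" while in the study.

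For sham patients entering Phase II, the protocol says "The results of the 6 months will serve as their new baseline results for phase II of the study".

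**The concern.** Needing an injection or surgery on the study knee is an event after randomisation, and it is plausibly tied to the outcome being measured. Under the rule, the protocol itself creates the missing value; the patient need not have wished to leave. The 6-month difference among patients with data can then depart from the difference between the groups as randomised.

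What is at stake is bias. The 10% allowance in the sample size protects precision and does nothing about who is missing. Scores that are not collected cannot be recovered by any later analysis.

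Phase II is touched as well. A sham patient withdrawn before month 6 has no Phase II baseline, and the within-group changes in Phase II rest on those who remain.

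**Working it through.** **What the documents supply.** They give 60 patients per arm, a 10% loss allowance not split by arm or reason (60 x 0.90 = 54 per arm), and an assumed effect of 0.8 SD. They give no rate of injection or surgery and no outcome for these patients, so there is no figure of the plan's own to reproduce on this point. Everything below is an assumed range.

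**Definitions.** Let w be the share of an arm withdrawn under this rule before month 6. Let g be how much less the withdrawn patients would have improved from baseline to 6 months than those who stay in the same arm, in SD of change. The comparison considered is a simple one among patients with a 6-month score, with no use of 3-month scores.

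**Formula.** If the patients who stay improve by S on average, the arm as randomised improves by (1 - w)S + w(S - g) = S - wg. Patients with data therefore overstate their arm by wg, and

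bias in (active minus sham) = w(active) x g(active) - w(sham) x g(sham).

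A minus sign means against the device.

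| w active v sham | g active, sham | Calculation | Bias (SD) |
|---|---|---|---|
| 10% v 10% | 1, 1 | 0.10 - 0.10 | 0 |
| 2% v 5% (about 1 v 3 of 60) | 1, 1 | 0.02 - 0.05 | -0.03 |
| 5% v 15% (3 v 9 of 60) | 1, 1 | 0.05 - 0.15 | -0.10 |
| 15% v 5% | 1, 1 | 0.15 - 0.05 | +0.10 |
| 10% v 10% | 0.5, 1.5 | 0.05 - 0.15 | -0.10 |
| 10% v 10% | 1.5, 0.5 | 0.15 - 0.05 | +0.10 |
| 5% v 15% | 0, 0 | 0 - 0 | 0 |

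Unequal rates alone do no harm if g is 0, and equal rates do not protect if g differs by arm. Against 0.8 SD, 0.03 is 0.03/0.8 = about 4% and 0.10 is 12.5%. The 5% v 15% case is an upper one: 3 + 9 = 12 of 120 uses the whole 10% allowance for this single reason.

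**Dependence on the estimand.** If the target is the effect regardless of injection or surgery, g is the gap after that intervention. Take 5% v 15%, with patients 1 SD worse before the intervention. If they gain 0, 0.5, 1 or 1.5 SD from it, g is 1, 0.5, 0 or -0.5 and the bias is -0.10 x g = -0.10, -0.05, 0 or +0.05 SD.

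**Power.** With 54 per arm and a two-sided t-test at 0.05, power is 98.5% at 0.80 SD, 97.7% at 0.77 SD and 95.0% at 0.70 SD. Loss of power is not the issue.

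Results stay in SD units because the plan's SD of 3.60 is for pain scores and is not stated to be for WOMAC.

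**The case against.** The strongest case against acting has four parts.

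- **Rates may be low.** Patients are told to refrain from injections. The -0.10 SD case needs a threefold difference in rates, a full 1 SD shortfall and the entire loss allowance. The milder case is 0.03 SD. This stands, and it limits how serious the point is.
- **Earlier scores are kept.** Only further collection stops, so a patient withdrawn after the 12-week visit keeps a 3-month WOMAC. An analysis using it could reduce the bias. This stands for those patients, but the plan does not say such an analysis will be done, and a patient withdrawn before that visit has only a baseline score.
- **Later scores reflect the rescue.** If the gain from an injection or surgery offsets the earlier deficit, collecting the scores may not move the estimate. This also stands, but only collected data can show whether it is so.
- **The plan never chose an estimand, so bias has no fixed reference.** This stands in part. Which estimand should be primary is a matter on which statisticians differ. Stopping collection, however, leaves no observed scores after the event for any estimand that needs them.

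A reader might also infer that the two sections on surgery contradict each other, since one has surgery recorded and dated and the other ends data collection. They can be read in sequence (the event is recorded, then follow-up stops), although the protocol does not say so.

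**Conclusion.** The point holds in conditional form. As written, the rule loses 6-month scores after an event plausibly linked to outcome, and nothing in the analysis text offsets it. The resulting bias is 0 if rates and shortfalls match across arms. In the assumed cases with 1 SD shortfalls it runs from 0.03 to 0.10 SD in size, in either direction. These figures rest on assumed rates, assumed g and a comparison that ignores 3-month scores.

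Several stronger readings are not supported:

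- **That the rule favours the device or raises the false-positive rate.** With a device that has no effect, this would need more withdrawals, or a larger shortfall, on the active arm. The documents give no reason to expect that while patients are blinded. If sham patients are withdrawn more often and would have done worse, the bias runs against the device.
- **That everyone using rescue is lost.** NSAIDs and physical therapy are listed as rescue but do not trigger withdrawal; only injection or surgery on the study knee does.
- **That Phase II improvements are overstated.** This follows only if withdrawn patients would have changed less than those who stay.

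The change is worth making because it is cheap and the loss is irreversible, not because a large bias has been shown.

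**What to change.** Data collection and analysis only; treatment, crossover and other clinical management are left as they are.

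**Subject Withdrawal.** Replace the clause that ends data collection with: *The date and type of the intervention are recorded, and WOMAC, VAS, SF-36 and adverse events continue to be collected at the research visits already scheduled for the patient's group, unless consent is withdrawn.* This also settles how the recording of surgical interventions fits with the withdrawal rule.

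**Data Analysis.** State that:

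- all randomised patients are analysed by assigned group with all observed scores, including the 3-month score when the 6-month score is missing (for example in a repeated-measures model), and how a patient with no score after baseline enters;
- scores after an injection or surgery are treated in a named way under the chosen estimand, with the other handling given as a sensitivity analysis;
- the number and timing of these events are reported by arm.

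**Cost.** The change needs protocol wording and questionnaires at visits already in the schedule. The downside is that scores after an injection or surgery partly reflect that intervention, which the stated estimand must acknowledge. For example, at 5% v 15% with a 1 SD gain from the intervention, the effect regardless of it is (0.15 - 0.05) x 1 = 0.10 SD smaller than the effect without it.

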Statistical Methodology	The analysis of power is performed conservatively by assuming the largest variability in pain scores observed in the preliminary data (e.g., reduction of pain scores of 3.0 in active group and 0 of control group with a pooled standard deviation of 3.60 corresponds to an effect size of 0.8. After accounting for a 10% loss to follow-up we would expect to enroll 60 patients in each group for a total of 120 patients. With 120 samples (60 each), the two-sided t-test will have 80% power at the 0.05 significance level to detect differences of pain score of 0.8 SD units between control and case

CONFIDENTIAL

This material is the property of the NYU School of Medicine and Langone Medical Center. Do not disclose or use except as authorized in writing by the study sponsor

I. PURPOSE OF THE STUDY AND BACKGROUND

Purpose

The purpose of this study is to examine the efficacy of AposTherapy® versus a control group, in the short-term at 6 months and in the long-term at 12 months post-treatment, with the primary efficacy assessment based on improvement in knee pain score and improvement in function in patients following diagnosis of knee osteoarthritis (OA).

Background & Study Rationale

With the rising incidence of osteoarthritis (OA) in today's aging population, increased attention has been directed toward the management of this debilitating disease. OA ranks as the number one most expensive condition among Medicare patients over the age of 65 [Cutler, 2012]. For knee osteoarthritis, total knee arthroplasty remains an effective and successful treatment option, with well over 700,000 total knee arthroplasties (TKA's) performed annually in the United States [CDC 2010]. Despite the popularity of TKA, the progression of knee OA to end stage degenerative joint disease requiring surgery can take a considerable amount of time to manifest [Kalunian, 2014]. Before surgical options are considered, more conservative measures are initially prescribed in the management of patients with knee OA, with non-pharmacologic physical therapy and lifestyle modifications being the first line treatment.

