A wide variety of physical therapies have been evaluated for knee OA, ranging anywhere from personalized exercised programs to gait kinematic analysis and correction [Abbott, 2013; Jones, 2013; Della Croce, 2013]. In particular, a biomechanical approach to reducing pain within a patient's knee can involve off-loading the diseased compartment, as well as promote focused muscle strengthening, thereby providing additional dynamic stability to the knee. For patients with mild varus deformities, some mixed success has been reported, such as the use of lateral wedged insoles. In these studies, the knee adduction moment was successfully reduced, demonstrating the biomechanical success of the insoles. However, the results regarding the correlation to pain reduction were mixed, though it has exhibited promise and prompted suggestion of modest improvement in pain and function [Jones, 2014; Skou, 2013].

AposTherapy is a non-invasive solution to restore normal knee kinematics during gait and activities of daily living. Through a personalized gait analysis, a patient's shoes are customized to adjust the ground reaction forces transmitted to the knee. This theory is in parallel with the biomechanical approach to lessen the moment arm responsible for loading on the patient's diseased and symptomatic knee compartment. In addition, the shift in external forces of the corrected gait pattern, induced by the biomechanical device, challenges neuromuscular control of the surrounding dynamic stabilizers of the knee and in turn can condition a more coordinated motor response [Bar-Ziv, 2010; Haim, 2011]. AposTherapy patients can also potentially experience more than biomechanical advantages. Having dedicated equipment for exercising can serve as a reminder, where AposTherapy patients can gain a psychological edge in the motivation of maintaining a physically active and healthy lifestyle. With the proper application of this biomechanical device, this study aims to evaluate the effect of AposTherapy® on pain and function as compared to a control group who receive a non-calibrated biomechanical device. Successful use of the AposTherapy® device can potentially decrease pain and improve function in patients with established OA, while encouraging a more active and healthy lifestyle.

Study Design

The study will be divided into two phases:

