Secondary Efficacy Endpoints

- Phase I:
 - Improvement in WOMAC scores between all study time points – pre-treatment and following 3 months and 6 months post-treatment;
 - Improvement in Visual Analog Score (VAS) score between all study time points;
 - Improvement in Short-Form 36 (SF-36) score between all study time points;
 - Reduction in usage of pain killers or NSAIDS
- Phase II:
 - Original Active group - Improvement in knee pain and knee function scores, as measured by change from baseline WOMAC score to 12 months post treatment;
 - Original Active group - Improvement in VAS score between baseline and 12 months post treatment;
 - Original Active group - Improvement in SF-36 score between baseline and 12 months post treatment;
 - Original Active group - Reduction in usage of pain killers or NSAIDS
 - Cross-over group - Improvement in WOMAC scores between all study time points – pre-treatment and following, 3 months and 6 months post-treatment;
 - Cross-over group - Improvement in Visual Analog Score (VAS) score between all study time points;
 - Cross-over group - Improvement in Short-Form 36 (SF-36) score between all study time points
 - Cross-over group - Reduction in usage of pain killers or NSAIDS

CONFIDENTIAL

This material is the property of the NYU School of Medicine and Langone Medical Center. Do not disclose or use except as authorized in writing by the study sponsor

Outcome Measure Evaluation Criteria

Western Ontario and Mac Master University (WOMAC) – the WOMAC is a self-administered osteoarthritis outcomes instrument designed to assess lower extremity pain and function in osteoarthritis of the knee or hip. The minimal clinically important difference (MCID) proportion is a 16.0% reduction in WOMAC [Hmamouch, 2014].

Visual Analog Score (VAS) Scale - the VAS is a validated pain scale that asks subjects to rate the amount of pain they are currently experiencing on a line up to 100mm (no pain is equal to 0mm and the worst imaginable pain is equal to 100mm). An improvement of 20 points from the baseline score is considered a statistically significant improvement at that visit [Gallagher, 2001].

Short-Form (36) Health Survey – the SF-36 is a patient reported survey of health that is designed to measure health status. The survey consists of eight (8) sections, where the lower the score the more disability and the higher the score the less disability [Maruish, 2009].

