During the baseline visit, the Apostherapy® team will meet with the patient to set them up with their device. Utilizing state-of-the-art technology, an in-depth analysis consisting of step length; load distribution on each leg; walking velocity; and gait symmetry, will be obtained. A personally-calibrated device will not be used for patients randomized to this group. The patient will receive a sham-placebo foot-worn biomechanical device. During their daily routine, patients will be asked to wear their custom-worn device for approximately 2 hours per day, up until the 6 month follow-up visit, starting with less than an hour of walking around the house and gradually increasing wearing time to outdoor walking. Patients will be asked to come to follow-up visits at the treatment center (located at [name]) at the following time points: 3 -4 weeks, 7 weeks, 12 weeks, 18 weeks, 24 weeks, 27 weeks, 36 weeks, 42 weeks and 52 weeks. During these visits the biomechanical device will be adapted according to the clinical needs of the patient (this will have no actual effect on the biomechanical device, since there are no biomechanical element in the sham device).

Phase I Study Visits

Patients will be followed for 6 months after enrollment. Patients will be seen for a screening/baseline visit and will then return to NYULMC (the physician's office) for a follow-up visit at, 3 months and 6 months from initial visit.

VISIT 1/2 - Screening/Baseline visit (the screening/baseline assessments may be completed in more than one session):

The following procedures will be conducted at the physician's office located at NYULMC Center for Musculoskeletal Care, [name]:

- Sign Informed Consent Document;
- Review Inclusion/Exclusion Criteria;
- Randomize patient to one of two study arms;
- Review and document demographics, medical/surgical/concomitant medication history (complete data collection form);
- Physical Knee Evaluation (will include the following, but not limited to):
 - Pain: Note location and activities that increase and decrease symptoms, joint line tenderness, etc.
 - Knee Effusion: Presence or absence

CONFIDENTIAL

This material is the property of the NYU School of Medicine and Langone Medical Center. Do not disclose or use except as authorized in writing by the study sponsor

- Ligament Stability: Anterior drawer test, posterior drawer test, lachman test, pivot shift, valgus/varus stress test.

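### The power statement assumes, without a reason, no change on sham; what the design offers is 80% power for a net difference of 0.54 SD (1.96 points at SD 3.60), which leaves room for about 1 point of sham improvement

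*Combined protocol and SAP*

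**What the plan says.** The Statistical Methodology row of the Study Summary and the Sample Size Analysis in section III carry the same calculation. The planning case is "reduction of pain scores of 3.0 in active group and 0 of control group with a pooled standard deviation of 3.60", described as an effect size of 0.8. Allowing for 10% loss to follow-up, the plan enrolls 60 per arm, and then states: "With 120 samples (60 each), the two-sided t-test will have 80% power" at the 0.05 level for a difference of 0.8 SD. It also says: "The analysis of power is performed conservatively by assuming the largest variability in pain scores observed in the preliminary data".

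Neither place gives a reason for the zero or a figure for sham response. Neither says whether any control group in the preliminary data wore a sham. The Sample Size Analysis refers to a Table X of effect sizes, which is not in the text available to us.

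The Control Arm Process section gives sham patients the gait analysis and about 2 hours of daily wear, "starting with less than an hour of walking around the house and gradually increasing wearing time to outdoor walking". Their treatment-center visit weeks are the same as in the Active Arm Process section, with apparent adjustments to the device. Patients are un-blinded only at the 6-month visit, and Subject Withdrawal allows rescue acetaminophen.

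**The concern.** The comparator is a sham worn by blinded patients who report their own pain, receive the same contact and walking schedule as the device arm, and enter only with VAS pain of at least 3. Some improvement in that arm is plausible. If it occurs while the device change stays at 3.0, the difference between arms is smaller than the planning difference, and the stated power does not describe the comparison that the trial will make.

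The stake is interpretation. A reader who takes the trial as powered for a 3.0-point contrast with sham could read a null result as a firm negative when it reflects sham improvement. The printed 80% adds to the difficulty, because it is not the power that the plan's own inputs give.

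**Working it through.** **Inputs.** Device change 3.0, control change 0, SD 3.60, two-sided 0.05 and 10% loss come from the Sample Size Analysis; 1:1 allocation comes from Randomization Process. Evaluable per arm: 60 × 0.9 = 54. The section names no scale for the pain score; 0-10 is assumed from the entry criterion.

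**Method.** Two-sample t-test with power from the noncentral t distribution, 2n − 2 degrees of freedom, noncentrality d / √(2/n), where d = (device change − sham change) / SD.

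**The plan's own figure.** 3.0 / 3.60 = 0.833, which the plan gives as 0.8.

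| d | 60 per arm | 54 per arm |
|---|---|---|
| 0.8 | 99.1% | 98.5% |
| 0.833 | 99.5% | 99.0% |

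The stated 80% does not reproduce. For 80% power at d = 0.8, 26 per arm are enough, or 26 / 0.9 = 28.9, so 29 enrolled. Using a one-sided test, or a two-sided level of 0.025 or 0.01, does not bring power near 80%; the lowest value is 93.5% (two-sided 0.01, 54 per arm, d = 0.8).

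**Net difference with 80% power.**
- 54 per arm: d = 0.544, and 0.544 × 3.60 = 1.96 points. Normal-approximation check: (1.960 + 0.842) × √(2/54) = 0.539, or 1.94 points.
- 60 per arm: d = 0.516, or 1.86 points.

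**Sham improvement at which power reaches 80%, device change held at 3.0.**
- 54 per arm: 3.0 − 1.96 = 1.04 points.
- 60 per arm: 3.0 − 1.86 = 1.14 points.
- Reading the effect as exactly 0.8 SD (SD 3.75, or a device change of 2.88) moves these to 0.92–0.96 and 1.02–1.07 points.

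**Power against assumed sham improvement (SD 3.60).**

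| Sham improvement | Net difference | 54 per arm | 60 per arm |
|---|---|---|---|
| 0 | 3.0 | 99.0% | 99.5% |
| 0.5 | 2.5 | 94.7% | 96.5% |
| 1.0 | 2.0 | 81.6% | 85.5% |
| 1.1 | 1.9 | 77.6% | 81.8% |
| 1.5 | 1.5 | 57.4% | 61.9% |
| 2.0 | 1.0 | 29.9% | 32.6% |

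**The case against.** Several defences of the text are sound.

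- **The 3.0 is already a difference between arms.** A reader might infer that the plan mistook a within-arm change for a treatment effect. Formally 3.0 − 0 is a net difference, and the power sentence concerns a contrast between arms. What remains is that one input to that contrast has no stated basis.
- **Conservatism is claimed only for the SD.** The sentence ties the word to the largest variability observed, so it does not misdescribe the assumed effect. Making the limit explicit is a clarification.
- **The zero may have been observed.** The text draws on preliminary data and a cited study that we cannot see, and it introduces the 3.0-and-0 case as an example. But no sham control is described there, so the point stays open.
- **The power table varies only the unfavorable input.** It holds the device change at 3.0 and the SD at its largest observed value. If the device change were larger by the same amount, the net difference and the power would not move. With assumed SDs of 3.0 or 2.5, which the documents do not give, the tolerated sham improvement would be 3.0 − 0.544 × 3.0 = 1.37 or 3.0 − 0.544 × 2.5 = 1.64 points.
- **The Background does not predict a sham response.** It says that "patients can gain a psychological edge in the motivation of maintaining a physically active and healthy lifestyle", but as a possible benefit to AposTherapy patients. Extending it to sham wearers would be our inference, and the point does not rely on it.

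None of this supplies a reason for the zero or makes the stated 80% correct.

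**Conclusion.** The point stands as a correction to the power statement. The control change of zero is unjustified. The stated 80% at 0.8 SD is really about 98% to 99%, and that surplus is what lets the design absorb roughly 1 point of sham improvement before power drops below 80%. These figures rest on SD 3.60, a device change held at 3.0, 10% loss and a 0-10 score. The sham range of 0 to 2 points is an assumption.

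A reader might go further and infer that zero is wrong, or that it is the most favorable value possible. The documents contain no sham-response figure that would show it to be wrong, and a control arm that worsened would be more favorable still. Nor does the point show that the trial is too small: at a net difference of 2.0 points, power is still 82% with 54 per arm.

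The calculation covers a pain score only. The Phase I primary endpoint is WOMAC pain and function, for which no power is given.

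**What to change.** In the Study Summary and the Sample Size Analysis, replace the 3.0-versus-0 planning case and its 80% claim with a statement of this kind: 60 enrolled (54 evaluable) per arm give 80% power, two-sided 0.05, for a net active-minus-sham difference of 0.54 SD, which is 1.96 points at SD 3.60 on a 0-10 pain score.

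In the same places:
- name the scale of the pain score;
- say that conservative refers to the SD only;
- show power against assumed sham improvement, as tabulated above, and give the source of any value taken as expected;
- note that the calculation does not cover the full WOMAC pain and function endpoint.

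The VAS criterion in Outcome Measure Evaluation Criteria ("An improvement of 20 points from the baseline score") should not be borrowed as the between-arm target. It describes a change within a patient on a secondary outcome, and its closeness to 1.96 points does not make it a difference between arm means.

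The cost is rewording in two places. The text would no longer present 3.0 points as the expected contrast with sham; sample size, conduct and analysis are unchanged.
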